## **4. GENERAL CONSIDERATIONS**

The statistical analysis will be performed using SPSS software vs 26.

Data will be generally provided with one decimal. In those cases that a greater accuracy is required, as much decimals as needed will be provided.

Adverse events will be codified using MedDRA dictionary (latest version available).

Continuous variables will be described by mean, median, standard deviation, minimum, maximum, Q1 and Q3. Categorical variables will be shown as distribution of frequencies and percentage

All available efficacy and safety data will be included in data listings and tabulations. No imputation of values for missing data will be performed unless otherwise stated. Data that are potentially spurious or erroneous will be examined according to standard data management operating procedures.

## 5. STUDY POPULATIONS

### 5.1. Definition of study populations to analyze

The following describes the different populations that will be used in the analyses process:

[figure not shown]
- **Efficacy population:** consists of all patients included in this study that received at least one dose of study treatment and have at least one evaluation visit after receiving the first dose of treatment. The efficacy population will be the basis for the primary endpoint analysis in this study. This will also be the patient population used for the analysis of the secondary endpoints.
- **Safety population:** consists of all patients who received at least one dose of the study treatment and had at least one valid post baseline safety assessment.

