## **10.2. Study treatment visits**

Study patients will be evaluated weekly during the first 2 months and every 2 weeks thereafter.

The following procedures will be performed during study treatment:

- Tumor evaluation: PET-CT, CT and/or MRI (every 8 weeks)
- Physical examination: will be performed at screening and thereafter targeting symptoms in subsequent study visits
- Ophthalmological examination: Ask patient for changes in vision at every visit. If change in vision is reported, an ophthalmological examination must be performed preferably within 3 days. Ophthalmologic examination will be performed weekly during first cycle, biweekly during second cycle and every 4 weeks thereafter. Particularly for patients who experience any decrease in visual acuity, or symptomatic or asymptomatic retinal disorders including retinal detachment / RPED / serous retinopathy / retinal vein occlusion (Grade 1 analog to CTCAE v.5) have to undergo ophthalmologic examinations on day 1 of every cycle.
- Weight: in all study visits

- Vital Signs: pulse, blood pressure and temperature; every week during first two cycles, and days 1 and 15 of each cycle thereafter
- ECOG performance status (day 1 of every cycle)
- 12-lead ECG: if clinically indicated
- ECHO/MUGA: before start binimetinib treatment, 4 weeks after the start of treatment and every 12 weeks thereafter.
- Hematology: every week during first two cycles, and days 1 and 15 of each cycle thereafter
- Biochemistry: every week during first two cycles, and days 1 and 15 of each cycle thereafter. Safety laboratory tests can be collected up to 2 days prior to drug administration.
- TSH, fT3 y fT4: day 1 of every cycle. Free T3 and free T4 will only be measured if TSH is abnormal.
- Coagulation: day 1 of every cycle
- Urinalysis: day 1 of every cycle
- Serologies: if clinically indicated
- Pregnancy Testing: every 4 weeks (day 1 of each cycle). Pre-menopausal women of childbearing potential only
- Adverse events: in all study visits
- Concomitant medications: in all study visits
- Blood sample: two CPT tubes of 7 ml will be obtained before treatment administration at D1C1 and D1C2.

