## **11.3. Reporting procedures**

### **11.3.1. Reporting of adverse events (AEs)**

The investigator will try to obtain information about any adverse events that have occurred in all visits by examining or directly interrogating the patient. All information referring to adverse events must be recorded in the respective section of the CRF. AEs should be recorded according CTCAE v5.0. All adverse events that occur during the period comprehended from the start of study treatment to 30 days after last dose of the investigational products will be recorded. When one or more signs or symptoms correspond to a disease, the main diagnosis or syndrome will be notified. All adverse events will be followed until resolution or stabilization, or until it is determined that the study treatment or the patient's participation in the study has not been the cause. All adverse events still present at the end of the study period will be monitored until their final outcome is determined.

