### 12.3. Analytical Populations

Safety population consists of all patients included in this study who received at least one dose of study treatment.

The efficacy population will be the basis for the primary endpoint analysis in this study; it consists of all patients included in this study that received at least one dose of study treatment and have at least one evaluation visit after received the first dose of treatment. This will also be the patient population used for the analysis of the secondary endpoints.

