### 3.7. Total number of subjects

It is expected to include 25 patients in this trial. Patients diagnosed of metastatic or locally advanced non-curable TNBC that have received one or two treatment regimens for advanced disease will be included in this study.

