## 9. SAFETY ASSESSMENT

### 9.1. Safety Assessment; general considerations

The assessment will be performed for safety population defined in [section 5.1](#). Adverse events will be evaluated according to NCI CTCAE vs 5 criteria. Adverse events will be coded by the latest available version of MedDRA dictionary. AEs will be evaluated with the MedDRA code by system organ class (SOC) and preferred term (PT).

The analysis will be performed with the information completed into the adverse event eCRF section.

The analysis of adverse events will be performed per patient, for that the maximum grade for each adverse event completed of each patient will be calculated.

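### The SAP narrows the protocol's safety population with an undefined post-baseline condition, so a dosed patient who dies or is lost very early may be left out of the safety tables

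*SAP*

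**What the plan says.** Protocol section 12.3 sets a single condition: "Safety population consists of all patients included in this study who received at least one dose of study treatment".

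SAP section 5.1 sets two. It keeps the dosing condition and adds another, that the patient "had at least one valid post baseline safety assessment". The SAP does not define valid, does not say what counts as a safety assessment, and does not explain the departure from the protocol. SAP section 3.3 names protocol version 3.0 as current, and the SAP's revision history is empty.

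The narrower set is the one used. SAP section 9.1 states: "The assessment will be performed for safety population defined in", with a pointer to SAP 5.1. Sections 9.2 to 9.5 (adverse events, adverse reactions, serious events, events of special interest) follow from it. On the data source, section 9.1 adds: "The analysis will be performed with the information completed into the adverse event eCRF section".

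**The concern.** Safety is a secondary objective, and the protocol's definition depends only on having been dosed. The SAP's extra condition depends on what happens after dosing, so inclusion can be related to early outcome. A dosed patient with no assessment that qualifies as valid would leave both numerator and denominator, and very early severe toxicity is one reason for having none.

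The SAP has no fallback set of all dosed patients. Its efficacy population also requires a post-dose evaluation visit, and that set is used for baseline data (SAP 6.1) and exposure (SAP 7.1). A patient who was dosed but never assessed could fall outside both defined populations. With about 25 patients, one omitted event can change what the safety tables appear to show.

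**Working it through.** The plan states no figure for this point, so there is nothing to reproduce. The check compares the texts and then illustrates the size.

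**Who could be affected**

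- Protocol 11.3.1 sets the recording period: "All adverse events that occur during the period comprehended from the start of study treatment to 30 days after last dose". An event in the first days of treatment is therefore recorded.
- Protocol 10.2 sets the visits: "Study patients will be evaluated weekly during the first 2 months and every 2 weeks thereafter". In the section 10 schedule the first visit after day 1 is day 8, with a window of ± 2 days, so day 8 − 2 = day 6 to day 8 + 2 = day 10.
- A patient who is dosed and then dies or is completely lost before that visit can have a recorded event but no scheduled post-baseline assessment. Under Protocol 12.3 she is in the safety population. Under SAP 5.1 she is in only if the recorded event or death is itself accepted as a valid assessment.

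**Inputs for the illustration**

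- Planned number: "It is expected to include 25 patients in this trial" (SAP 3.7). Assume all 25 are dosed and none is replaced.
- k = number of dosed patients excluded by the SAP condition, each with the event of interest. Neither document gives k. I show k = 0 to 3 as an assumed range; 0 or 1 is the realistic part of it.
- x = number of the 25 dosed patients with the event.

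**Formulas**

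- Protocol rate = x/25.
- SAP rate = (x − k)/(25 − k).
- Intervals are exact (Clopper-Pearson) 95%.

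**Results**

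| k | Events among 25 dosed | Protocol definition | SAP definition |
|---|---|---|---|
| 0 | any | x/25 | x/25, no change |
| 1 | 1 | 1/25 = 4.0% | 0/24 = 0.0% |
| 1 | 3 | 3/25 = 12.0% | 2/24 = 8.3% |
| 2 | 2 | 2/25 = 8.0% | 0/23 = 0.0% |
| 3 | 3 | 3/25 = 12.0% | 0/22 = 0.0% |

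For one event in one excluded patient, the 95% interval is 0.1% to 20.4% for 1/25 and 0% to 14.2% for 0/24. The second upper limit can be checked by hand: 1 − 0.025^(1/24) = 0.142.

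**Direction**

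If the excluded patient did not have the event, the reported rate rises slightly: 1/25 = 4.0% becomes 1/24 = 4.2%. The rate falls only when the excluded patient had the event. That is the likelier case for very early departures, but it is not certain.

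**The case against.** The strongest reply is that few patients, perhaps none, would be lost.

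- **Wording.** SAP 5.1 asks for an evaluation visit in the efficacy definition but only a safety assessment in the safety definition. A recorded adverse event or death could reasonably count as an assessment, and then no recorded harm drops out. This is a fair reading, but the SAP does not state it, and the word valid leaves the decision to judgement at analysis.
- **Withdrawal for toxicity.** A reader might infer that patients who stop early for toxicity disappear from the tables. The documents do not support that. Protocol 8.2 requires withdrawal procedures and follow-up of the adverse event, Protocol 10.3 specifies an early-withdrawal visit with examination, laboratory tests and adverse events, and Protocol 11.3.4 extends follow-up to early withdrawals. Such patients would ordinarily have a post-baseline assessment. A patient hospitalised elsewhere would usually have a later visit too.
- **Hidden deaths.** A reader might also infer that an early fatal event would go unreported. That is unlikely. SAP 5.5 reports deaths during the study without naming a population and describes those due to adverse events or reactions in detail. SAP 5.4 covers discontinuations, and SAP 5.3 promises to explain differences between analysed and recruited numbers. Separately, Protocol 11.1.3 keeps deaths from progression out of the serious adverse events whichever population is used.
- **General data rule.** SAP section 4 promises that all available safety data will be listed and tabulated. This softens the problem, but it conflicts with the restricted set named in SAP 9.1 and does not override it.

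These points limit the exposure mainly to death or complete loss before about day 6 to day 10, in patients who had to have ECOG 0-1 and a life expectancy above 24 weeks. They do not remove the contradiction. An early death could be counted under SAP 5.5 and be absent from the section 9 percentages, so the SAP's own tables would disagree.

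**Conclusion.** The point holds as a contradiction between protocol and SAP that may affect the safety tables. That the two definitions differ, and that section 9 uses the narrower one, is certain from the text.

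The consequence is conditional. It needs a dosed patient with no scheduled post-dose assessment and a reading of valid assessment that does not accept a recorded event or death. The number of such patients is not in the documents and is probably 0 or 1. If there are none, the results do not change. If there is one and she had an event, a rate of 4.0% (upper limit 20.4%) is reported as 0% (upper limit 14.2%). These figures assume 25 dosed patients and no replacements. The likely bias is towards a safer-looking combination.

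A claim that early harms will be removed, or that the bias must run one way, would go beyond the documents. The primary endpoint is not affected.

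**What to change.** In SAP section 5.1, delete the second condition of the safety definition (that the patient "had at least one valid post baseline safety assessment") together with the word joining it to the first. Use the protocol's definition, based on at least one dose of study treatment, for all section 9 tables.

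It would help to add that a dose of either binimetinib or palbociclib counts. That is a clarification: Protocol 12.3 does not spell it out, but it agrees with how SAP 7.2 dates the first dose. The change also removes the conflict with the general data rule in SAP section 4.

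If the sponsor prefers to keep the narrower set, the departure from the protocol should be justified, valid assessment defined (including whether a recorded event or death qualifies), and dosed patients outside the set listed with their events.

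The preferred change costs one SAP sentence, needs no new data, and should be made before database lock.

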### 5.2. Study recruitment period

The date of informed consent form for the first subject and the last subject included in the study will be provided.

### 5.3. Disposition of subjects

*Figure 1: Disposition of subjects*

\*Discrepancies between the number of analysed patients and number of recruitment patients into the database will be described.

The frequency distribution and percentage of patients analysed will be provided by site.

## 5.4. Study Discontinuations

Number and percentage of patients who discontinued the study and their reasons will be described. Those patients who leave the study for reasons related to study medication will be described in detail.

## 5.5. Deaths

Number and percentage of patients who died during the study and their reasons will be provided per treatment group. Patients who have died due to adverse events or adverse reactions will be described in detail.

# 6. SUBJECT DESCRIPTION

## 6.1. Demographic and baseline description. General considerations

All demographics and baseline characteristics will be described for efficacy population.

## 6.2. Subject Characteristics

### a) Demographics

The following variables will be described:

- Age, years (continuous).
- Ethnicity (categorical).

### b) Baseline characteristics

The following variables will be described:

- Vital signs:
  - Weight (Kg) (continuous).
  - Height (cm) (continuous).
  - Systolic blood pressure (mmHg) (SBP) (continuous).
  - Diastolic blood pressure (mmHg) (DBP) (continuous).
  - Pulse rate (b.p.m) (continuous).
  - Temperature (°C) (continuous).
- 12-lead ECG (Done/not done) (categorical), if performed:
  - Result (Normal/ abnormal not clinically significant / abnormal clinically significant).
- ECO/MUGA (Done/not done) (categorical), if performed:
  - Result (Normal/ abnormal not clinically significant / abnormal clinically significant).

- Hepatitis B surface antigen (Positive / Negative / Not done) (categorical).
- Hepatitis C antibody (Positive / Negative / Not done) (categorical).
- HIV (Positive / Negative / Not done) (categorical).

### c) Cancer history

The following variables will be described:

- Performance status at screening (ECOG-PS) (categorical).
- Time from initial diagnosis, defined as the elapsed time in months between the initial diagnose date to informed consent date (continuous).
- TNM & Stage at initial diagnosis (categorical).
- Current disease status (Advanced/Metastatic) (categorical).
- Time from advanced/metastatic disease, defined as the elapsed time, in months, between the advanced/metastatic disease date to informed consent date (continuous).
- Histology (categorical).
- Histologic grade (differentiation): GX: Grade cannot be assessed, G1: Well differentiated (Low grade), G2: Moderately differentiated (Intermediate grade), G3: Poorly differentiated (High grade), G4: Undifferentiated (High grade), Not Available (differentiation) (categorical).
- Actual TNM & Stage (categorical).
- Breast cancer previous treatments:
  - Previous surgeries (Yes/No) (categorical), if affirmative: surgery description by patient (categorical).
  - Previous chemotherapy-based treatment (Yes/No) (categorical), if affirmative:
    - Localized disease chemotherapy (Yes/No) (categorical), if affirmative: chemotherapy scheme by patient (categorical).
    - Metastatic disease chemotherapy (Yes/No) (categorical), if affirmative: chemotherapy scheme by patient (categorical).
  - Previous radiotherapy (as primary therapy) (Yes/No).
  - Previous hormonal therapy (Yes/No) if affirmative: hormonal treatment by patient (categorical).
  - Previous immunotherapy (Yes/No) if affirmative: immunotherapy treatment by patient (categorical).
  - Other previous treatments (Yes/No) if affirmative: treatment by patient (categorical).

**d) Baseline lesions:**

The analysis of target and non-target baseline lesions will be performed together.

It will be considered affected location when the patient presents at least one lesion in one organ or system, regardless of the number of lesions in the organ or system is more than one. It will be provided:

- The number and percentage of patients with each affected location (categorical).
- The number and percentage of patients by number of affected locations (categorical).

## **7. TREATMENT ADMINISTRATION**

### **7.1. Treatment description. General considerations**

The information related to treatment descriptions, dose intensity and subsequent treatments will be presented for the efficacy population defined in [section 5.1.](#)

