### 7.3. Dose intensity

Dose intensity will be defined as the total of each study drug received by the patient with respect to the exposure treatment time. The dose intensity will be described as mg/week.

The relative dose intensity will be defined as the total dose of each drug received by the patient in relation to the theoretical total dose that patient should had received per protocol.

The dose intensity and relative dose intensity will be evaluated as continuous variables.

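### SAP 7.1 puts exposure and dose-modification tables on the efficacy population while adverse events use the safety population, so the two can have different denominators and some treated patients can drop out of the dose tables

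*SAP*

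**What the plan says.** SAP 7.1 sets the population for the whole of section 7: "The information related to treatment descriptions, dose intensity and subsequent treatments will be presented for the efficacy population". Section 7.2 then covers cycles given, interruptions, reductions, the reasons for both, and exposure time. Section 7.3 covers dose intensity.

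SAP 5.1 admits a treated patient to the efficacy population only if she also satisfies this condition: "have at least one evaluation visit after receiving the first dose of treatment". What counts as an evaluation visit is not defined.

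For adverse events, SAP 9.1 says: "The assessment will be performed for safety population defined in" SAP 5.1. There the safety population is patients who "received at least one dose of the study treatment and had at least one valid post baseline safety assessment". Protocol 12.3 is wider and asks for one dose only: "Safety population consists of all patients included in this study who received at least one dose of study treatment".

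On dose intensity, SAP 7.3 gives an absolute measure ("The dose intensity will be described as mg/week") and a relative one. The relative measure divides by the "theoretical total dose that patient should had received per protocol". The SAP does not say whether that dose is fixed at the start or follows the changes that the protocol allows.

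**The concern.** Interruptions and reductions are tolerability results and are read next to the adverse-event tables. The two sets of tables rest on different entry rules, and the SAP gives no reason for describing exposure on an efficacy set. The serious-event and special-interest listings (SAP 9.4 and 9.5) record dose reduction, interruption or withdrawal as the action taken. A patient could be listed there with a dose action and be absent from the dose tables.

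The stake is moderate. Safety is a secondary objective, and Protocol 5.2 expects dose changes: it cites 61% of patients reduced to 30 mg BID in a melanoma study of binimetinib and notes toxicities that overlap with those of palbociclib. With 25 patients, one to three exclusions visibly shift a percentage. The undefined denominator of relative dose intensity adds a second uncertainty to the same tables.

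**Working it through.** The plan gives no computed figure on this point, so there is none to reproduce. The planned 25 patients (Protocol 12.2) serve only as a denominator.

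**Step 1: the sets side by side.**
- All treated (Protocol 12.3 safety population): at least one dose.
- SAP safety population (adverse-event tables): at least one dose and a valid post-baseline safety assessment.
- SAP efficacy population (dose tables): at least one dose and a post-dose evaluation visit.

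The second and third sets can differ from each other, and each can be smaller than the first.

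**Step 2: effect on the percentage with a dose reduction.** Inputs: N = 25 treated (planned number), x = 10 with a reduction (assumed), k = 0 to 3 treated patients outside the efficacy population (assumed). The all-treated value is x/N = 10/25 = 40.0%. The value shown is (x − k)/(N − k) if all the excluded had a reduction, and x/(N − k) if none had.

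| k | all excluded had a reduction | no excluded patient had one |
|---|---|---|
| 0 | 10/25 = 40.0% | 10/25 = 40.0% |
| 1 | 9/24 = 37.5% | 10/24 = 41.7% |
| 2 | 8/23 = 34.8% | 10/23 = 43.5% |
| 3 | 7/22 = 31.8% | 10/22 = 45.5% |

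Varying x at k = 3:
- x = 5: 20.0% becomes 2/22 = 9.1% or 5/22 = 22.7%.
- x = 15: 60.0% becomes 12/22 = 54.5% or 15/22 = 68.2%.

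**Step 3: relative dose intensity.** The starting doses are those in SAP 3.10. Assumed: six 28-day cycles (24 weeks), dose change from cycle 2, no missed doses.
- Binimetinib scheduled: 6 × 28 × 90 = 15,120 mg. Received with 30 mg BID from cycle 2: 28 × 90 + 5 × 28 × 60 = 10,920 mg. Against the starting dose: 10,920/15,120 = 72.2%. Against a denominator adjusted for the reduction: 100%. Absolute: 10,920/24 = 455 mg/week against 15,120/24 = 630.
- Palbociclib scheduled: 6 × 21 × 100 = 12,600 mg. With 75 mg from cycle 2: 2,100 + 5 × 21 × 75 = 9,975 mg, or 79.2%. With 125 mg from cycle 2: 2,100 + 5 × 21 × 125 = 15,225 mg, or 120.8%. Both are 100% on an adjusted denominator.
- Mean palbociclib value against the starting dose with 10 escalated, 10 reduced and 5 unchanged: (10 × 1.2083 + 10 × 0.7917 + 5)/25 = 100%. Escalations cancel reductions, so escalated patients need a separate line.

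A third reference is possible. The dose table in Protocol 9.3.1 labels 125 mg palbociclib as the recommended dose and 100 mg as the first reduction, whereas Protocol 6.1 and SAP 3.10 start at 100 mg. Against 125 mg, a patient kept at 100 mg scores 12,600/15,750 = 80%. These passages must be reconciled. This point takes no view on the dose itself.

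**Step 4: why a flat weekly rate will not serve as the reference.** Palbociclib averages 100 × 21/4 = 525 mg/week. A patient who stops at day 21 on full dose has taken 2,100 mg. The flat rate expects 525 × 3 = 1,575 mg and gives 2,100/1,575 = 133%. The dosing calendar expects 2,100 mg and gives 100%.

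**The case against.** The best case for the plan is that the gap between the populations is probably small and that other outputs cover it.
- Visits are weekly for two months (Protocol 10.2), so few treated patients would lack any post-dose visit.
- SAP 8.2 provides for efficacy patients with no tumour assessment, which suggests that an evaluation visit need not include a scan. Even if it must, Protocol 10.3 requires a scan when treatment stops for a reason other than progression.
- SAP 5.3 to 5.5 describe discrepancies between recruited and analysed patients, discontinuations with reasons, and deaths. Stops related to study medication are to be described in detail.
- Reduction counts and mg/week do not use the relative denominator, so a reduced patient in the tables remains visible on either reading.

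All of this stands and limits the size of the problem. It does not explain why exposure should be described on an efficacy set, and it does not give the dose and adverse-event tables a common denominator.

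A reader might also infer that SAP 7.3 uses a denominator that moves with the dose rules. The documents do not establish this. The wording speaks of a theoretical total dose, and SAP 3.10 describes only the fixed starting doses. The adjusted denominator is one possible reading, and the defect is that the SAP does not choose.

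**Conclusion.** The mismatch is explicit in SAP 7.1 and 9.1 and is worth correcting. It does not touch the primary analysis. With 25 treated and 10 reduced, excluding 1 to 3 patients moves 40% to 31.8–37.5% or to 41.7–45.5%. With no exclusions nothing changes. The numbers reduced and excluded are assumptions. Replacement under Protocol 8.3 could also take the number treated above 25.

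Two stronger conclusions are tempting and not supported. One is that tolerability will look better than it is: the direction depends on whether the excluded patients had dose changes, and for palbociclib an adjusted denominator lowers the score of an escalated patient (120.8% to 100%). The other is that the dose and adverse-event tables will certainly disagree: if any visit counts as an evaluation visit, the two SAP populations nearly coincide.

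The relative dose intensity point is secondary and is one of ambiguity. It matters most for binimetinib, which has no step above 45 mg BID, so adjusting the denominator for allowed reductions can only raise the result (72.2% to 100% in the six-cycle example).

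**What to change.** 1. In SAP 7.1, replace the efficacy population by all patients who received at least one dose, citing Protocol 12.3.
2. In SAP 5.1, align the safety population with Protocol 12.3 by removing the requirement for a post-baseline safety assessment. Without this second edit the dose tables would cover all treated patients and the adverse-event tables possibly fewer.
3. In SAP 7.3, state that relative dose intensity is measured, as a reporting reference only, against the cumulative dose scheduled at the protocol starting doses on the 21/7 calendar (palbociclib) and the continuous calendar (binimetinib) up to the end of treatment, not against a flat mg/week rate. Report patients escalated above the starting dose separately. Because Protocol 9.2 allows one drug to continue alone, also state whether the scheduled dose of the stopped drug keeps accruing.

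The cost is SAP wording and table shells, to be settled before database lock. No treatment rule changes and no new data collection is needed, since Protocol 8.2 already asks for data up to withdrawal, including the date of last treatment. Reported percentages may move in either direction.
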